1 INTRODUCTION

1.1 Indication

Bacterial vaginosis (BV) is the most common cause of foul-smelling vaginal discharge in females of reproductive age. Other symptoms that may be present include vaginal itching or a burning sensation while urinating. It is estimated that BV affects between 10% to 30% of heterosexual women^{1,2} and 20% to 50% of homosexual women.³⁻⁷ The prevalence varies between populations and have been reported to be as high as 50% in parts of Asia and Africa.⁸ Further, it is estimated that BV contributes to over 60% of vulvovaginal infections and may cause preterm delivery, increase the risk of transmission of HIV and other sexually transmitted infections, and lead to increased stress and reduced quality of life.^{9,10} Diagnosing BV clinically usually involves, apart from gynecological examination, vaginal sampling which is tested for fishy odor after addition of a 10% potassium hydroxide (KOH) solution, increased pH (> 4.5), and presence of clue cells. These criteria, including presence of discharge, constitute the Amsel criteria¹¹ and is confirmatory of diagnosis in the majority of cases.¹²

The vaginal microbiome is a dynamic system with a complex mixture of microorganisms in different ratios and quantities, which depend on lactic-acid producing bacteria to maintain a weakly acidic environment, see overview.¹³ Bacterial vaginosis is characterized by a shift in the vaginal microbiota and a high species diversity. There is an increased presence of facultative anaerobes, which leads to a rise in vaginal pH, which can be accompanied by a depletion of *Lactobacillus* species.¹⁴ Up to 50% of patients experience recurrence within 1 year following treatment,⁹ often leading to repeated treatment with antibiotics, which further adds to the issue of antibiotic resistance.¹⁵ The high recurrence rate can be explained by the inability of conventional antibiotics, such as metronidazole, to fully eradicate the biofilm that forms in BV. The polymicrobial microfilm that develops in BV is dominated by *Gardnerella vaginalis*, *Mobiluncus spp.*, *Bacteroides spp.*, *Prevotella spp.* and *Atopobium vaginae*.^{14,16} Biofilms are only temporarily suppressed by antibiotic treatment and rapidly regain activity upon treatment cessation.¹⁶ In addition, vaginal or systemic antibiotics treatment is frequently followed by vulvovaginal candidiasis, likely due to the elimination of the protective bacterial flora, thereby allowing *Candida* overgrowth.¹⁷⁻²¹

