3.2 Rationale for Study Design

As described in [Section 1.1](#), BV is a major clinical concern, and new effective interventions not associated with antibiotic resistance and major drug interactions would be valuable additions to the current treatment arsenal. This study aims to investigate the clinical performance and safety of the Gedea Pessary containing GDL and NaG in treating BV.

Previous *in vitro* data show that GDL inhibits both bacterial and fungal biofilm formation (see [Section 1.2](#)). In addition, a device comparable to Gedea Pessary with regards to its pH-lowering and biofilm-inhibiting properties, have shown high BV cure rates.³⁸ Data also indicate that GDL is tolerable and does not pose any special risk to humans ([Section 1.3.1](#)).

Based on this, it may be argued that a trial involving patients is justified due to the widespread clinical problem of BV and the issues involving current therapies (see [Section 1.1](#)). Further, due to that the pessary has not been evaluated clinically prior to this study and the lack of proper comparators, a single-arm design has been chosen, allowing evaluation of clinical performance in a smaller number of patients. The risk of introducing assessor bias due to the open-label design have been minimized by the use of well-defined and documented scales, as well as objective laboratory assessments.

The dose of 300 mg GDL and 376.5 mg NaG administered 2 days apart on Day(s) 0, 2, 4, and 6^a was chosen based on pre-clinical data, specifically an *in vitro* dissolution test of the Gedea Pessary using a vaginal fluidic model (see IB). Measurements of pH in the *in vitro* dissolution test showed a pH-decrease duration of approximately 45 hours.

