3.5 Study Visits and Procedures

3.5.1 Day 0; Screening and Enrollment

Patients seeking treatment for symptoms relating to BV may be informed about the study, and, if agreeing to participate, sign the informed consent form (ICF). After enrollment, patients will have gynecological examinations performed, where the Investigator or an authorized designee will assess the presence of BV according to Amsel's criteria and bacterial culturing from a vaginal swab, as described in [Section 6.1](#).

If the Investigator assesses that the patient has BV, based on examination and fulfillment of 3 out of 4 Amsel criterion, the patient will receive the investigational product to be self-inserted vaginally at home on Day 0. Additional doses will also be dispensed to be administered by patients on Day(s) 2, 4, and 6. Two (2) vaginal secretion samples will also be collected by swab. One (1) of the samples will be cultured to verify presence of bacteria and 1 sample will be taken and used for sequencing analysis of the vaginal microbiome ([Section 7.2](#)). Symptoms of BV (fishy smell, irritation, and burning) and AEs, if any, will be collected.

Procedures performed:

- Informed consent
- Eligibility criteria
- Pregnancy test (urinary)
- Recording of:
 - medical history,
 - concomitant medication, and
 - adverse events
- Gynecological examination by Investigator or an authorized designee evaluating diagnosis of BV according to Amsel's criteria:
 - Presence of thin, white, homogenous discharge
 - Presence of clue cells on microscopy (more than 20% of epithelial cells)
 - pH of vaginal fluid above 4.5
 - Release of fishy odor "i.e. a positive whiff test" when alkali (10% potassium hydroxide [KOH] solution) is added
- Symptoms of BV (fishy smell, irritation, and burning) evaluated by patients according to a scoring scale (0-3)
- Vaginal swab for:
 - culture, and
 - sequencing
- Treatment dispensing and self-administration by patients

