3.5.5 Day 7 (+2 Days); Follow-up Visit

Patients will visit the clinic on Day 7 to have gynecological examination performed where the Investigator or an authorized designee will assess the presence of BV according to 3 Amsel criteria. Vaginal samples will be collected by swab to be used for vaginal microbiome sequencing analysis and vaginal pH assessed for product *in vivo* duration.

If BV symptoms are still present according to Amsel's criteria, patients will have prolonged treatment and receive additional doses of investigational product to be administered at home on Day(s) 7, 9, 11, and 13.

In addition, patients will be asked questions from the patient questionnaire to assess: symptoms of BV (fishy smell, irritation, and burning); usability; concomitant medications; and AEs, if any.

Procedures performed:

- Gynecological examination by Investigator or an authorized designee assessing the presence of BV according to the following Amsel criteria:
 - Presence of thin, white, homogenous discharge
 - Presence of clue cells on microscopy (more than 20% of epithelial cells)
 - Release of fishy odor "i.e. a positive whiff test" when alkali (10% potassium hydroxide [KOH] solution) is added
- Symptoms of BV (fishy smell, irritation, and burning) evaluated by patients according to a scoring scale (0-3)
- Vaginal swab for sequencing
- Vaginal pH
- Recording of:
 - concomitant medications,

- adverse events, and
- usability
- Treatment dispensing and self-administration by patients if receiving prolonged treatment

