5 TREATMENTS

5.1 Investigational Product

The investigational product, Gedea Pessary (commercial name *pHyph*), is a GDL-and-NaG containing pessary to be administered vaginally with a CE-marked vaginal tablet applicator (Schägner GmbH, Steinmauern, Germany). The device is intended to treat vaginal bacterial and Candida infections, see [Figure 2](#) and [Figure 3](#) for product image and applicator label. Gedea Pessary is a Class IIa medical device according to MDD 93/42/EEC (the Swedish regulation SFS 1993:584 and LVFS 2003:11).

NOTE: The terms investigational product, Gedea Pessary, investigational device, pessary, and vaginal pessary are used interchangeably in the CIP.

Gedea Pessary is a white, convex, bullet-shaped tablet, approximately 2 cm in length, contract-manufactured by Galenica AB (Malmö, Sweden). The pessary is slow-release formulated, administering 300 mg GDL and 367.5 mg NaG over 45 hours. Each patient will administer a total of 4 pessaries in the study or 8 if receiving prolonged treatment. The investigational products will be packed in blister packs containing 4 pessaries labeled with *Gedea Pessary* and batch number. Blisters will be packed together with 4 vaginal tablet applicators in a cardboard-box labeled with *Gedea Pessary, for investigational use only*, production date, and expiry date ([Figure 4](#)).

It is the responsibility of the Investigator to ensure that the investigational products are stored in their original packaging in a secure location with access only by authorized personnel, separate from other medications. The investigational product shall be stored at room

temperature (15°C-25°C), protected from direct sunlight or freezing. The investigational products *must not* be used outside of the study. For further reference, refer to the IB.

Instructions for use will be distributed at the first visit, advising patients on how to use the product together with the applicator. Briefly, patients will be instructed to: wash their hands and vaginal area prior to use; place a tablet into the applicator and insert as far into the vagina as is comfortable (without forcing), or until half of the applicator is inside; discard the applicator after use; not use tampons or other vaginal products while using this product.

[figure not shown]
Figure 2 Gedeo Pessary and Applicator

Figure 3 Vaginal Tablet Applicator Label

Figure 4 Investigational Product Label

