7.2 Clinical Laboratory Evaluation

Vaginal samples will be collected by vaginal swab on Day(s) 0 and 7 (and Day 14 if receiving prolonged treatment) by the Investigator and on Day 35 (or Day 42 if receiving prolonged treatment) by patients. Collected samples will be used accordingly:

- Samples collected on Day 0 will be sent to laboratory and cultured to confirm the BV diagnosis. Time for lab results is approximately 1 week.
- Samples collected on Day(s) 0, 7, 14, and 35 or 42 will be analyzed to assess the effects of the investigational product on the vaginal microbiome before treatment, after the treatment series, and at study end. Collected samples will be sent to laboratory sequencing present bacterial DNA content for complete species overview.

Patients' vaginal pH will be measured for assessments of investigational product *in vivo* duration on Day(s) 0 and 7. Vaginal pH lower at Day 7 compared to Day 0 indicate appropriate release duration.

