7.10.1 Extent of exposure

See Section 7.8 above. Furthermore, as a measure of investigational product *in vivo* duration, patients' vaginal pH will be assessed on Day(s) 0 and 7. Vaginal pH lower at follow-up visits compared to Day 0 indicate appropriate release duration. Summary statistics on the vaginal pH will be presented.

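### A Day 7 vaginal pH below the Day 0 value does not show that the pessary's release lasts as long as intended, so that inference should come out of both documents

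*Protocol*

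**What the plan says.** Protocol 7.2 has vaginal pH measured on Days 0 and 7 to assess how long the product acts in vivo, and gives the interpretation in advance: "Vaginal pH lower at Day 7 compared to Day 0 indicate appropriate release duration". SAP 7.10.1, under extent of exposure, says the same with a broader time reference: "Vaginal pH lower at follow-up visits compared to Day 0 indicate appropriate release duration". Tables 2 and 3 of the Protocol schedule pH on Days 0 and 7 only.

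Protocol 5.1 describes the pessary as "administering 300 mg GDL and 367.5 mg NaG over 45 hours". The 45 hours comes from an in vitro dissolution test, which according to Protocol 3.2 "showed a pH-decrease duration of approximately 45 hours". On dosing before the reading, Protocol 3.5.1 says: "Additional doses will also be dispensed to be administered by patients on Day(s) 2, 4, and 6". The visit itself is headed "3.5.5 Day 7 (+2 Days); Follow-up Visit". Any further pessaries for women not cured are handed out at that visit for use at home, so the Day 6 dose is the last one before the reading.

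On the disease, Protocol 1.1 says: "There is an increased presence of facultative anaerobes, which leads to a rise in vaginal pH". A pH above 4.5 is one of the four Amsel criteria, of which three are required for entry (Protocol 4.2). Vaginal pH is an exploratory endpoint summarised descriptively (SAP 7.9.3), and its change from Day 0 to Day 7 is derived (SAP 8.4).

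**The concern.** The table of pH values is only descriptive, but its meaning is fixed beforehand: any fall counts as support for the release duration. Two other explanations of a fall are built into the design. One is recovery from BV. The other is regression to the mean in women who were raised on this measure at entry. Without a control arm neither can be separated from residual product. The reading is also not tied to the number of hours since the last pessary, although duration is a statement about hours.

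Protocol 1.3.2 says the device has not been tested in an earlier clinical trial, and the plan contains no other in vivo check of release. If the sentence were followed, the report could present an in vitro figure as clinically confirmed by data that cannot confirm it.

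**Working it through.** **The plan's own figure.** The 45 hours is an in vitro measurement whose data are in the Investigator's brochure. It cannot be recomputed from the Protocol or SAP and is taken as given.

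**Timing.** Hours from the Day 6 dose to the pH reading are

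h = 24 × (visit day − 6) + visit clock time − dose clock time.

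Neither document gives clock times. Two ranges are therefore shown. The first assumes a dose between 06:00 and 24:00 and a clinic visit between 08:00 and 17:00. The second makes no assumption, so the two clock times may differ by anything from −24 to +24 hours.

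| Visit day | Assumed hours: shortest | Assumed hours: longest | No assumption | Against 45 h |
|---|---|---|---|---|
| 7 | 24 + 8 − 24 = 8 h | 24 + 17 − 6 = 35 h | 0 to 48 h | Before 45 h under the assumed hours |
| 8 | 48 + 8 − 24 = 32 h | 48 + 17 − 6 = 59 h | 24 to 72 h | Either side |
| 9 | 72 + 8 − 24 = 56 h | 72 + 17 − 6 = 83 h | 48 to 96 h | Always after |

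Day 8 depends on when the woman doses:

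- Dose 06:00 to 09:00: 48 + 8 − 9 = 47 h to 48 + 17 − 6 = 59 h, all beyond 45 h.
- Dose 20:00 to 24:00: 48 + 8 − 24 = 32 h to 48 + 17 − 20 = 45 h, none beyond.

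The Day 9 result needs only that the Day 6 dose is taken on Day 6.

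**What each reading can show.** At 8 to 35 hours a low pH is compatible with release that stops at 36 hours as well as with release that lasts 45, so it does not establish the duration. After 45 hours the stated release has ended, so a low pH needs another explanation, and a pH that has not fallen does not show that release was too short. The inference fails in both directions.

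**Recovery and release.** Protocol 1.1 has BV raising pH. The expected consequence, which is an inference and not a sentence in the Protocol, is that resolution lowers it. A pessary whose release ended early but which cleared BV could therefore satisfy the stated interpretation. SAP 7.9.3, 7.10.1 and 8.4 contain no split of pH by cure status or by time since dose. SAP 7.1.4 uses the case report form visits as analysis visits, so readings on Days 7, 8 and 9 are summarised together.

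**The case against.** The best defence is that little hangs on this sentence. It sets no threshold, required proportion or hypothesis. pH is exploratory, lies outside the cure definition and enters no success criterion. That stands, and it limits the point to an interpretation that should not be drawn. It does not rescue the interpretation, which both documents state plainly.

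It is also fair that the nominal visit is on Day 7, when release should still be running, and that 45 hours is approximate. Both stand. But a reading during release shows acidity at that hour, not how long release goes on.

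A reader might go further in several ways that the documents do not support:

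- **That release is over on two of the three permitted days.** This is certain only for Day 9. Day 8 depends on clock times that are not given.
- **That about 17 of 24 women would show a fall from cure alone** (0.70 × 24 = 16.8). This assumes that pH falls in every cured woman. The cure definition leaves pH out, and neither document says how pH behaves in cured women.
- **That every woman enters with a raised pH.** It is one of four criteria with three required, so a woman may qualify without it. Regression to the mean applies to those who do have it, and their number is not stated.
- **That the dosing interval depends on this reading.** Protocol 3.2 rests the interval on the in vitro test, and nothing in the plan feeds the Day 7 pH back into it.

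**Conclusion.** The concern holds, as a minor one. A lower pH at the Day 7 visit cannot indicate appropriate release duration in this design, because recovery and regression to the mean also favour a fall and no permitted visit day makes the reading a test of 45 hours. The effect is confined to one exploratory conclusion. The primary cure rate, its confidence limit and the sample size are untouched.

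The conclusion rests on the stated 45 hours, on the Day 6 dose being taken on Day 6, and on the inference from Protocol 1.1 that resolving BV lowers pH. The 8 to 35 hour figure for Day 7 rests on assumed dosing and clinic hours. Without that assumption the range is 0 to 48 hours, so a Day 7 reading could pass 45 hours only with a dose soon after midnight and a late-evening visit.

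A reader might think the claim could be saved by limiting it to uncured women examined within 45 hours. It could not. At the assumed 70% cure rate about 7 women would be uncured (24 − 16.8 = 7.2). The restriction conditions on an outcome that release may itself affect, and a reading before 45 hours still cannot show that release lasts that long.

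**What to change.** - Delete the release-duration inference from Protocol 7.2 and SAP 7.10.1, and state that no conclusion on in vivo release duration will be drawn from vaginal pH.
- Report pH at the Day 7 visit and its change from Day 0 descriptively, by actual visit day (7, 8 or 9) and by cured or not cured. Visit day follows from the analysis relative day in SAP 7.1.3. A split at 45 hours would need dose clock times, which neither document shows to be collected.
- Reconcile the plural follow-up visits in SAP 7.10.1 with the schedule, which has only one pH reading after Day 0.

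The cost is two deleted sentences and a split of an existing descriptive summary, with small numbers in some cells. The trial gives up a claim of in vivo support for release duration.

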7.3 Untoward Medical Events / Adverse Events

The definitions are the definitions in the current version of the ISO 14155. The categorization will adhere to the following table in ISO 14155;

Table 4 Untoward Medical Events / Adverse Events Categorization

ADVERSE EVENTS	Non-device related	Device-or-procedure related	
Non-serious	Adverse Event (AE) ^a (3.2)	Adverse Device Effect (ADE) (3.1)	
Serious	Serious Adverse Event (SAE) ^b (3.37)	Serious Adverse Device Effect (SADE) (3.36)	
		Anticipated	Unanticipated
		Anticipated Serious Adverse Device Effect (ASADE) (3.42, Note)	Unanticipated Serious Adverse Device Effect (USADE) (3.42)

References in parentheses refer to sections in the standard ISO 14155:2011

^a Includes all categories.

^b Includes all categories that are serious

Adverse events are any untoward medical occurrence, unintended disease or injury, or untoward clinical signs (including abnormal laboratory findings) in subjects, users or other persons, whether or not related to the investigational medical device.

The AE may be directly related to the use of an investigational medical device and are then called an adverse device effect (ADE). This includes events due to insufficient or incomplete instructions, use, implantation, or dysfunction of the tested product. Misuse and errors while using the product are also included in the ADE definition.

The following events are not considered untoward medical events / AEs:

- Medical interventions planned before study initiation given that the status of the participant has not worsened since signing the consent form or the intervention has had to be done at an earlier date.
- All conditions or diseases known at the time when the subject signs the informed consent form, are not considered untoward medical events / AEs. These will be registered in the medical history CRF page.

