1.3.2 Clinical Data

The GDL-and-NaG-containing investigational device, *Gedea Pessary* (commercial name *pHyph*), has not been tested in previous clinical trials. Products containing polymerized lactic acid have comparable properties to Gedea Pessary, as lactic acid and GDL have the same ability to inhibit bacterial biofilm formation and lower the pH to a similar extent, see IB. One such product, *Laccure Pessary* (Laccure AB, Helsingborg, Sweden), is buffered to pH 3.5, whereas Gedea Pessary is buffered to pH 3.6. Laccure Pessary has been tested in a clinical trial of 126 patients with confirmed BV, where 93 patients were treated with 1 or 2 doses of Laccure Pessary and 33 patients formed the control group.³⁸ The study showed an 80% cure rate for the single-dose treatment. Most adverse events (AEs) reported were of mild intensity and brief. The most common event was vaginal itching, experienced less than 20% of patients. No serious adverse events (SAEs) occurred and the treatment had no visually detectable negative impact on the vaginal mucosa.

Based on published studies on current treatments for BV, oral, topical, and intravaginal antibiotics are generally well tolerated; reported AEs include nausea, headache, diarrhea, vaginal discharge, and vulvovaginal pruritus. The reported frequencies of AEs after treatment with antibiotics are between 4.6% to 42%, depending on antibiotic used and route of administration.^{16,25,27,39}

Collectively, pre-clinical data indicate that GDL and NaG are safe and may be an effective topical treatment for BV, and a GDL-and-NaG-containing slow-release pessary is to be investigated in this clinical trial.

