2 STUDY OBJECTIVES

2.1 Primary Objectives

To investigate the clinical performance, tolerability, and safety of the investigational product.

Primary endpoints:

- Clinical cure rate on Day 7
 - Defined as absence of all of the following Amsel criteria:
 1. Thin, white, yellow, homogenous discharge
 2. Clue cells on microscopy (more than 20% of epithelial cells)
 3. Release of fishy odor “i.e. a positive whiff test” when alkali (10% potassium hydroxide [KOH] solution) is added
- Safety and tolerability, based on reported treatment-emergent AEs

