3.3 Recruitment

Patients will be recruited at study sites' gynecological clinics. Post-menarchal, pre-menopausal females 18 years or older seeking for BV symptoms (fishy smell, irritation, and burning) may be informed verbally and in writing about the study and screened following signed informed consent. Patients may also be pre-informed about the study by the use of advertisement through social media; these patients will directly book appointments with the clinic. The recruitment of patients will start only after the approval of the clinical investigation plan (CIP) by the regulatory authorities (RA) and the independent ethics committee (IEC). No study procedures will be performed unless the patient has provided written informed consent to study participation. See also [Section 4.1](#).

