9.1 Statistical Analysis

The clinical performance endpoints will be presented with the appropriate point estimate together with the 95% confidence interval. Any possible statistical testing will be performed using an overall significance level of 5%.

Although there are two co-primary endpoints, no adjustment of e.g. p-values or confidence intervals will be applied. This is for two reasons, the first being that the evaluation of the second co-primary endpoint (safety and tolerability) will only be based on descriptive statistics and data listings, and the second is that both co-primary endpoints have to show favorable results. For all other statistical analyses of the secondary endpoints, no adjustment due to multiple testing will be performed.

Statistical analysis will be based on all data, however, results will also be presented by site.

If the stated assumptions that the statistical evaluation is built upon can be questioned, suitable alternative methods may be applied. For example, a 95% confidence interval based on a non-parametric method may be applied if assumption of data belonging to the normal distribution seems not to hold. This, together with further details on the statistical analysis and identification of any possible exploratory or subgroup analysis, will be given in the SAP.

Sensitivity analyses may be performed to evaluate the robustness of the results.

Any deviations or changes to the study protocol specified statistical analyses will be documented and justified in the SAP and the Clinical Investigation Report (CIR).

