7.10.2 Adverse Events

Adverse events will be coded according to MedDRA.

Only treatment-emergent adverse events, i.e. adverse events starting after administration of first dose of study treatment, will be presented as described below. Any adverse events reported to start before administration of first dose of study treatment will be listed separately. In the remainder of this section, the term "adverse event" should be interpreted as "treatment-emergent adverse event".

An overview of all adverse events will be presented, including the number and percentage of patients with at least one, and the total number, of the following:

- Adverse events.
- Serious adverse events.
- Adverse events leading to withdrawal of the investigational product.
- Fatal adverse events.
- Adverse events, broken down by severity (intensity).
- Adverse events, broken down by causality assessment (relationship).

The International Organization for Standardization (ISO) terms ADE, SADE, ASADE, USADE introduced in the CIP constitute adverse events where relationship to investigational device or study procedure is indicated. The classification of an untoward medical event as USADE or ASADE will be done retrospectively. The event will initially be captured as a serious adverse event.

The incidence of adverse events will be presented by system organ class and preferred term. For each system organ class and preferred term, the total number of adverse events as well as the number and percentage of patients with at least one adverse event in that system organ class or preferred term will be presented. The incidence of serious adverse events will be presented in the same way.

Separate tables for the incidence of adverse events broken down by severity and the incidence of adverse events broken down by causality assessment will also be presented by system organ class and preferred term.

There will also be tables on the most frequently reported adverse events, on system organ class level and on preferred term level. The decision on the frequency cut-off for these tables will be taken during the analysis of the adverse events data in consultation with the author of the clinical study report and could be influenced by factors such as the overall number of adverse events, study design, and the nature of the indication. The frequency cut-off should be mentioned in a table note.

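### Worsening of irritation or burning already present at consent falls outside the adverse event rules, so the safety and tolerability co-primary may capture it incompletely and inconsistently

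*Protocol*

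**What the plan says.** Protocol 7.3 lists two kinds of event that are not adverse events. The first is an intervention planned before the study, and it is excluded only "given that the status of the participant has not worsened since signing the consent form" (or, in effect, if it has not had to be brought forward). The second is broader: "All conditions or diseases known at the time when the subject signs the informed consent form, are not considered untoward medical events". These go to the medical history page, and nothing is said about worsening.

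SAP 7.10.2 defines treatment-emergent events as "adverse events starting after administration of first dose of study treatment". Events that began earlier are listed separately and stay out of the summary tables.

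The second co-primary endpoint is "Safety and tolerability, based on reported treatment-emergent AEs" (Protocol 2.1). Protocol 7.10 and 9.2.3.1 base tolerability on adverse events. Protocol 9.1 gives the co-primary weight by requiring that "both co-primary endpoints have to show favorable results".

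Protocol 3.3 describes the women to be approached as "seeking for BV symptoms (fishy smell, irritation, and burning"). Each symptom is scored 0 to 3 by the patient at Day 0 and at every later contact (Protocol 3.4 and Appendix 1).

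**The concern.** Two of the three presenting symptoms, irritation and burning, resemble what a local reaction to an acidic vaginal pessary could look like. For the comparable lactic acid pessary, Protocol 1.3.2 reports: "The most common event was vaginal itching, experienced less than 20% of patients". Consider a woman with mild burning at Day 0 and severe burning after dosing. Her burning was known at consent, so Protocol 7.3 excludes it. It began before the first dose, so SAP 7.10.2 does not count it either.

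What is at stake is the direction of error in a co-primary endpoint. Events lost this way can only make tolerability look better, and a single-arm study has no control group in which under-capture would show. An event never recorded as an adverse event during the study also loses its severity and causality ratings, which are hard to reconstruct afterwards.

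**Working it through.** The point rests on wording, and the plan states no figure to reproduce. The first four steps compare the provisions. The last is an illustration on assumed inputs.

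**1. The two exclusion bullets (Protocol 7.3).** Planned interventions carry a worsening condition; known conditions carry none. With a clause in one bullet and not in the next, the plain reading is that a known condition stays excluded even when it worsens.

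**2. The SAP definition (7.10.2).** It depends on start date alone. If an investigator does record worsened burning, the result depends on the date entered. Dated from first appearance, it goes to the separate pre-dose listing. Dated from the worsening, it enters the tables. The SAP does not say which date to use.

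**3. The symptom scores.** They are handled as clinical performance variables (Protocol 6.1, 9.2.2; SAP 7.9.2), and no section sends a worsened score into adverse event reporting. The endpoint is the three-item sum, which can hide a worsened item:

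| | Smell | Burning | Irritation | Sum |
|---|---|---|---|---|
| Day 0 | 3 | 1 | 0 | 4 |
| Day 7 | 0 | 3 | 0 | 3 |

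The change is 3 − 4 = −1. Under SAP 8.7 this woman counts as having a reduction, although her burning has become severe. The separate items are summarised descriptively, but the SAP text specifies no within-patient shift for them.

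**4. What is still captured.** Irritation or burning that first appears after dosing is an adverse event under both documents. Withdrawals from the study or from treatment are listed among the tolerability and safety assessments (Protocol 9.2.3; SAP 6.2).

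**5. Illustration of size.** Let q be the true rate of new or worsened irritation or burning, and f the share of women who already have the symptom at consent. Neither is in the documents. Assume that reactions are equally likely with and without baseline symptoms, and that every reaction in a woman with baseline symptoms goes unrecorded. Then:

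- expected number counted = 24 × q × (1 − f)
- chance of counting none = (1 − q(1 − f))^24

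| f | q = 10% | q = 20% | q = 30% |
|---|---|---|---|
| 0 (nothing lost) | 2.4 (8%) | 4.8 (0.5%) | 7.2 (0.02%) |
| 25% | 1.8 (15%) | 3.6 (2%) | 5.4 (0.2%) |
| 50% | 1.2 (29%) | 2.4 (8%) | 3.6 (2%) |
| 75% | 0.6 (55%) | 1.2 (29%) | 1.8 (15%) |

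Cells give the expected number of women counted, of 24, with the chance of counting none in brackets. Example: 24 × 0.20 × 0.50 = 2.4, and 0.90^24 = 0.08.

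For any given q and f these are upper bounds on the loss from the reporting rule, because they assume that no investigator reports worsening.

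**The case against.** The strongest reply is that the text does not make capture nil. Protocol 7.3 opens with a broad definition covering any untoward medical occurrence. Protocol 7.5.2 tells investigators to report when in doubt, Protocol 7.6 also draws events from examination findings, and Appendix 1 asks an open question about health problems at each contact. An investigator could reasonably treat marked worsening as a device reaction rather than as the known condition. This stands. A reader might infer that worsened symptoms are never counted; the documents support only incomplete and inconsistent capture. It does not remove the gap, because a general instruction for doubtful cases does not override an explicit exclusion, and the SAP filter applies in any case.

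Three other inferences go too far:

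- **That tolerability has no other measure.** Withdrawal rates are listed alongside adverse events, and the usability questionnaire asks whether use of the tablet is gentle.
- **That every woman enters with irritation and burning.** Inclusion rests on Amsel criteria, neither symptom is one of them, and Protocol 1.1 describes itching and burning only as symptoms that may be present.
- **That the cited rate of under 20% measures the bias here.** It is a ceiling for itching with a different product, and itching is not among the scored symptoms.

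It is also fair to say that the co-primary is descriptive, with no threshold, and that item scores and patient listings will be available. A careful reader of the report could find worsening there, but it would not appear as tolerability.

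**Conclusion.** The gap is real in both documents. Read literally, worsening after dosing of irritation or burning already present at consent is left out of the adverse-event-based co-primary. Because practice may differ between investigators, the likely effect is incomplete and inconsistent capture, leaning towards favourable tolerability. New-onset symptoms, withdrawals and descriptive item scores are unaffected.

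The size cannot be established from the documents, which give no baseline prevalence of either symptom and no reaction rate for this product. The table shows what could be lost under assumed values and full non-reporting; it does not estimate the bias in this trial. The conclusion rests on the wording of Protocol 7.3 and SAP 7.10.2, and would stand with any other illustrative figures.

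**What to change.** 1. In Protocol 7.3, add to the second bullet: *unless the condition worsens in severity or frequency after the first dose*.
2. In SAP 7.10.2, define treatment-emergent as *starting or worsening after administration of first dose*. Without this, an event admitted by the Protocol could still be filtered out at analysis because of its original start date.
3. Add a supportive, descriptive table of shifts from Day 0 to each contact for the irritation and burning scores, with the number of women who rise by at least one grade. Keep it outside the co-primary: the same scores also reflect uncured bacterial vaginosis, so a rise is not by itself evidence of intolerance.

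The cost is two clauses, one table from data already collected, and a reminder to sites. The reported adverse event rate may come out slightly higher.
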